4 STUDY PLAN

4.1 Study Design

This is a multi-site (HUP, PPMC), unblinded, randomized, observational study performed in a controlled environment in the operating room. The hypothesis is that rapid sequence intubation or other urgent airway procedures performed with the biocontainment device will be safe and can be performed in an equivalent manner to urgent airway procedures without the biocontainment device. Methods to minimize bias include randomizing patients to intubation with or without the biocontainment device. Stratification of results will be performed as described in [Section 9.4.7](#) below.

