1.3 Schema

Week 1 through Week 4	Enrollment and Training

 • Total n=5 anesthesiologists, 10 CRNAs/anesthesia residents/fellows (user subjects) • Identify user subjects - anesthesiologists and their teams of CRNAs, anesthesia residents and fellows performing planned airway procedures under general anesthesia. • Obtain informed consent from willing user subjects and complete intake questionnaire • Document and record contact information for user subjects • Review user manual and device use. 	
Week 1 through Week 6	Device Use and Assessment

 • Protective device use and aerosol evacuation during airway procedures under general anesthesia on COVID-19-negative patients • Patients (patient subjects) of anesthesiologists participating as user subjects in the study will be recruited on the day of procedure. • Patient subjects will be randomized to intubation with or without the biocontainment device. • Goal of obtaining data from 150 airway procedures under general anesthesia in the device (100 with the device and 50 without the device). • Patient subject Data and data from record of airway procedure will be recorded after each device use • Quality Use Survey, including documentation of any AEs will be completed by user subjects at the end of each day • Patient experience questionnaire completed by patient subject randomized to device use within 1 week after procedure 	

- AE event summary reconciliation and review performed weekly
- Feedback on quality use data use and user suggestions given to engineering team every two weeks
- Interval assessment by the medical director of intubation data from medical record, quality use survey data, including summary of AEs, and preliminary analysis of post-training questionnaire/intake data every two weeks

Week 4 through Week 12	Device Use and Assessment, Final Data Analysis
	
• Continued use and assessment of biocontainment device if needed to meet enrollment numbers• Final Feedback on device use and user suggestions given to engineering team• Final assessment of survey data and device utilization

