5.5 Strategies for Recruitment and Retention

User Subject Recruitment and Retention

User-subjects will be recruited from within the department of anesthesia at HUP or PPMC. They will be approached in person or via email asking for participants in a trial of a biocontainment device for planned airway procedures under general anesthesia. Information provided will include length of time for study participation, participation in device training session, participant eligibility including willingness to use the device during procedures and lift up to 10 lbs, and participant requirements in the study (completion of surveys post-utilization and training). Healthcare workers (user subjects) will be recruited based solely on these criteria

and will include attending physicians, residents, fellows, and CRNA. No specific gender, age, race or ethnicity criteria will be used in the recruitment of subjects. Fifteen (15) to twenty (20) user subjects will be recruited at the study sites over the first month of the study. We anticipate full recruitment during this time. If targets are not met during the first month, recruitment will be ongoing during the second month of the study. Healthcare workers will be recruited solely on a voluntary basis with the option to withdraw at any time from the study without any form of penalty. The consent process will explicitly state that volunteering to participate in the study, declining to participate in the study, or withdrawal from the study will not affect employment status or access to appropriate PPE as determined by hospital protocols. This study is voluntary and no compensation or additional incentives will be provided.

Patient Subject Recruitment and Retention

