6.3 Measures to Minimize Bias: Randomization and Blinding

Randomization will be done to assign patients to intubation with or without the biocontainment device in a 2:1 fashion. This will allow for analysis of patient-related intubation factors as well as user-related intubation factors as part of the feasibility analysis. Blinding is not possible with this study as all users and patients will be aware of the presence of the device intervention. To help minimize bias in the data analysis, results of all data analysis will be assessed by a neutral, third-party with expertise in statistical analysis.

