8 STUDY ASSESSMENT AND PROCEDURES

8.1 Efficacy Assessments

User Subject Enrollment: Anesthesiologists (attendings, fellows, residents) and CRNAs who perform airway procedures under general anesthesia will be screened and recruited to the study as described in [Section 5](#) above. The anesthesia attendings work in teams with the residents and CRNAs and therefore, each anesthesia attending user subject will be assigned a unique identifier number and a unique biocontainment device that also has a unique ID number. This information will be collected as part of the device use forms to track the use of each device during the trial. User data to be collected includes first and last name, contact phone number and email address, age, gender, years of experience, healthcare degree, and training level.

User Subject Device Training: User subjects will undergo training on use of the biocontainment device as described in the Device preparation, use cleaning and storage **Section 6.2.4**. This will include in person or video demonstration of device use, review of a written user guide and an opportunity to setup and use a demo unit. Training will also include reviewing reporting any AEs, SAEs, ADEs or UADEs to the PI or qualified designee.

Patient Subject Recruitment: Patients who are undergoing airway procedures under general anesthesia who are assigned to the user subject's usual case-load will be recruited on the day of the procedure for the study. Inclusion and exclusion criteria will be as described above in Section 5. Recruitment will take place on the day of the procedure as cases and assigned providers can shift at the last minute and this will help ensure enrollment efficiency for patient subjects in the study. The on-site participation of the patient in the trial is limited to the actual scheduled procedure that includes an airway procedure under general anesthesia.

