9.4.6 Sub-Group Analyses

Primary and secondary endpoints will be analyzed in the context of gender (males versus females) age, and co-morbid conditions for patient subjects, and years of experience of the user subject.

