9.4.7 Tabulation of Individual Participant Data

Individual participant data will be listed by measure and by time point.

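### The primary time analysis has no term for attending or site, and Section 9.4.7, to which Section 4.1 refers for stratification, is only a data listing

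*Combined protocol and SAP*

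**What the plan says.** Section 4.1 describes how bias will be limited. Patients are randomised, and "Stratification of results will be performed as described in" Section 9.4.7. The whole of Section 9.4.7 reads: "Individual participant data will be listed by measure and by time point".

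The section before it, 9.4.6, does break results down: "Primary and secondary endpoints will be analyzed in the context of gender (males versus females) age, and co-morbid conditions for patient subjects", and also by the user's years of experience. It names neither attending nor site.

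On allocation, Section 6.3 says "Randomization will be done to assign patients to intubation with or without the biocontainment device in a 2:1 fashion", and the Section 1.3 schema aims for "100 with the device and 50 without the device". Sequence generation, blocking, strata and concealment are not described.

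On operators, the schema lists "Total n=5 anesthesiologists, 10 CRNAs/anesthesia residents/fellows (user subjects"), while Section 5.5 says "Fifteen (15) to twenty (20) user subjects will be recruited at the study sites over the first month of the study". Patients are drawn from the recruited anesthesiologists' caseloads (Section 5.5). Attendings work in teams, and Section 8.1 says "each anesthesia attending user subject will be assigned a unique identifier number and a unique biocontainment device".

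Section 9.4.2 compares procedure time between arms by ANOVA. It adds a multiple regression on user experience, number of prior device uses and patient factors.

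**The concern.** Time to secure an airway plausibly depends on who is in charge and which team does the work. Patients are clustered in a handful of attendings' lists, so attending is the obvious grouping factor. The one sentence that promises stratified results leads to a listing, and the section probably meant leaves this factor out.

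If the arms are unevenly spread over attendings, differences between attendings enter the device–control difference as noise. Under randomisation this is not systematic bias. It widens the confidence interval for the first primary endpoint and can shift the estimate in any one trial. A model term removes most of that at almost no cost, provided it is specified before the data are analysed.

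**Working it through.** **1. The cross-reference.** Section 4.1 concerns stratifying results, which is an analysis step. Section 9.4.7 has none. Section 9.4.6 has subgroups. A section number off by one is the likely explanation, though that is an inference. With the number corrected, attending and site are still absent from 9.4.6 and from both analyses in 9.4.2.

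**2. The plan's own sample size.** Section 9.2: 1.96² × 0.25 / 0.1² = 96.04, rounded up to 97. This reproduces. (The formula as printed, with 0.25 × 0.75, would give 72.03; the plan's next line uses 0.25.) The figure contains no allocation ratio, between-arm difference or operator variance, so nothing below changes it.

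**3. Inputs.**
- From the documents: n = 150, ratio 2:1 (100:50), 5 attendings.
- Assumed: 30 patients per attending (150/5), simple 2:1 allocation, and attending explaining a share ρ of the variance in time. The documents give no ρ, so I use 0.1, 0.2 and 0.3.

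**4. Benchmark.** With 20:10 within every attending and attending in the model, the variance of the difference, per unit of total variance, is (1 − ρ)(1/100 + 1/50) = 0.03(1 − ρ).

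**5. Simple allocation, attending ignored.** With T device and C control patients and m = 30 per attending, the expected variance is

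(1/T + 1/C) × [(1 − ρ) + ρ(n − m)/(n − 1)], where (n − m)/(n − 1) = 120/149 = 0.805.

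Averaged over Binomial(150, 2/3), 1/T + 1/C is 1.010 × 0.03. Relative to the benchmark:

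ratio = 1.010 × [1 + 0.805 × ρ/(1 − ρ)].

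**6. Simple allocation, attending in the model.** The variance is (1 − ρ)/Σ x(30 − x)/30, where x is the device count for each attending. The expected sum is 150 × 2/9 × 29/30 = 32.2, giving 1/32.2 = 0.0310, or 1.034 times 0.03. Averaging the reciprocal over simulated allocations raises this to 1.039, whatever ρ is.

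| Assumed ρ | Attending ignored | Attending in model | Inflation removed by the term |
|---|---|---|---|
| 0.1 | 1.10 | 1.04 | 6 of 10 points |
| 0.2 | 1.21 | 1.04 | 17 of 21 points |
| 0.3 | 1.36 | 1.04 | 32 of 36 points |

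A separate simulation gave 1.09, 1.21 and 1.34 with attending ignored, and about 1.03 with it in the model. On the standard error, 1.10 and 1.36 correspond to +5% (√1.10 = 1.049) and +17% (√1.36 = 1.166). At ρ = 0.05 the ratio is 1.05, so there the term gains little.

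**7. What blocking adds.** Once attending is in the model, only the step from about 1.03–1.04 to 1.00 is left for blocking.

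**8. The overall split.** Under simple allocation the device arm has a 95% range of 89–111. The average cost is the factor 1.010, about 1% in variance. Drift toward equal arms helps: 89:61 has 0.92 times the variance of 100:50, and 111:39 has 1.16 times.

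**The case against.** Several points on the other side stand.

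- **Analysis wording.** Section 4.1 speaks of results. A reader might infer that it promises stratified randomisation which was then omitted. The text does not say that.
- **Silence on method.** A reader might take the bare 2:1 ratio to mean that allocation is unrestricted. Section 6.3 gives no method, so simple allocation is an assumption here.
- **Planned adjustment.** The regression on user experience and prior device uses may already absorb part of the operator effect. The ρ that matters is what remains between attendings after those covariates, and it may be below the range used. Experience still does not identify the attending, and the ANOVA has no such covariates.
- **Attending is not the hands-on operator.** Residents, fellows and CRNAs also perform the procedures. An attending term captures the team and its setting, not each pair of hands. Going down to individual users is costly: with 15 users of 10 cases each and simple allocation, adjusting for user gives about 1.12 times the variance of a design blocked by user. Attending plus the planned experience covariate is the reasonable compromise.
- **Blocking has a price.** The trial is unblinded. If block size were known, blocks of 3 at 2:1 would make 44% of assignments certain ((2/2 + 1/3)/3), and blocks of 6 would make 29% certain ((4/3 + 2/5)/6). Varying the size reduces this without removing it. Section 8.1 also says that assigned providers can change late, so some patients could be stratified under the wrong attending.
- **Feasibility study.** Section 4.2 calls this a safety and feasibility study, which limits the stakes.

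None of this supplies an attending or site term or repairs the reference.

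**Conclusion.** The concern holds in a limited form. The Section 4.1 reference is wrong, and neither the likely target nor the primary time analysis accounts for attending or site. With five attendings of 30 patients each, simple allocation and an attending share of 10–30% (all assumed), omission inflates the variance by about 9–34% in simulation and 10–36% by formula. An attending term leaves about 3–4%. Below a 10% share the gain is small. If attending explained nothing, the term would cost about 3% (1.039/1.010 = 1.028).

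Two stronger readings should not be drawn:

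- **That the device arm may fall short of a required 97.** Under simple allocation it would have fewer than 97 with probability 0.27. But Section 9.2 sets 97 as a count of procedures for the study, not for one arm, and derives it from a single-proportion margin of error unrelated to comparing times.
- **That blocking would deliver the main gain in precision.** Nearly all of the gain comes from the model term.

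**What to change.** 1. In Section 9.4.2, add attending as a factor in the primary time comparison, in both the ANOVA and the regression, beside the planned covariates. Add site as well if any attending works at both hospitals; the documents do not say that each is tied to one.
2. Record the attending's identifier for every procedure. Sections 6.4 and 8.1 attach it to the device-use forms and the Quality Use Survey, so state that it is also captured for procedures without the device.
3. In Section 4.1, replace the reference to 9.4.7 with the section that holds the stratified or adjusted analysis.
4. In Section 6.3, state how the sequence is generated and concealed, and whether blocks or strata are used. Optionally, use concealed 2:1 permuted blocks of varying size within attending, with a rule for late changes of provider.

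Items 1 to 3 cost a few sentences, one data field and 4 degrees of freedom out of 148, with no extra patients. Item 4 costs a paragraph. Its blocking option adds about 3–4% in variance beyond adjustment, against a small risk of predictable assignments. Allocation cannot be changed for patients already randomised, but the model term can still be added until the data are analysed.

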4.2 Scientific Rationale for Study Design

Briefly, the protocol is designed as a safety and feasibility study of airway procedures under general anesthesia using a biocontainment and aerosol evacuation device. The goal of the study is to refine device protocols and labelling with the goal of providing frontline healthcare workers additional protection.

4.3 End of Study Definition

A participant is considered to have completed the study if he or she has completed all phases of the study including the last user questionnaire after final use of the device as shown in the Schedule of Activities (SoA), Appendix [Section 12.1](#).

5 STUDY POPULATION

5.1 Inclusion Criteria

In order to be eligible to participate in this study, an individual must meet all of the following criteria:

A) User Subjects (healthcare workers):

1. Anesthesiologist, anesthesia resident, anesthesia fellow, or CRNA at the Hospital of the University of

Pennsylvania or PPMC who has signed and dated informed consent.

B) Patient Subjects:

1. Provision of signed and dated informed consent form
2. Stated willingness to comply with all study procedures and availability for the duration of the study
3. ASA I, II, III
4. Undergoing planned procedure involving an airway procedure under general anesthesia
5. Age 18 years or older

5.2 Exclusion Criteria

An individual who meets any of the following criteria will be excluded from participation in this study.

A) User Subjects (healthcare workers):

1. Pregnancy (due to potential risks from lifting the device)

B) Patient Subjects:

1. Known history of difficult airway
2. Anticipated difficult airway management for any reason
3. COVID-19 positive status
4. Planned prolonged intubation post-surgery or anticipated inability to answer patient questionnaire within 1 week of intubation.

5.3 Lifestyle Considerations

There are no associated lifestyle considerations required for patients participating in this study as their direct device involvement is limited to the single time in the device. No limitations on interactions outside of the hospital will be required by the device users or patients.

5.4 Screen Failures

Screen failures are defined as participants who consent to participate in the clinical trial but are not subsequently randomly assigned to the study intervention or entered in the study. A minimal set of screen failure information is required to ensure transparent reporting of screen failure participants, to meet the Consolidated Standards of Reporting Trials (CONSORT) publishing requirements and to respond to queries from regulatory authorities. Minimal information includes demography, screen failure details, eligibility criteria, and any serious adverse event (SAE).

5.5 Strategies for Recruitment and Retention

User Subject Recruitment and Retention

User-subjects will be recruited from within the department of anesthesia at HUP or PPMC. They will be approached in person or via email asking for participants in a trial of a biocontainment device for planned airway procedures under general anesthesia. Information provided will include length of time for study participation, participation in device training session, participant eligibility including willingness to use the device during procedures and lift up to 10 lbs, and participant requirements in the study (completion of surveys post-utilization and training). Healthcare workers (user subjects) will be recruited based solely on these criteria

and will include attending physicians, residents, fellows, and CRNA. No specific gender, age, race or ethnicity criteria will be used in the recruitment of subjects. Fifteen (15) to twenty (20) user subjects will be recruited at the study sites over the first month of the study. We anticipate full recruitment during this time. If targets are not met during the first month, recruitment will be ongoing during the second month of the study. Healthcare workers will be recruited solely on a voluntary basis with the option to withdraw at any time from the study without any form of penalty. The consent process will explicitly state that volunteering to participate in the study, declining to participate in the study, or withdrawal from the study will not affect employment status or access to appropriate PPE as determined by hospital protocols. This study is voluntary and no compensation or additional incentives will be provided.

Patient Subject Recruitment and Retention

Patient-subjects will be recruited from among the patients assigned to a recruited anesthesiologist's case-load. Given the constraints and timing of these assignments, the patient-subjects will need to be recruited on the day of the procedure. Patients will be approached by a study investigator or designee and asked about willingness to participate in study testing a new droplet and aerosol containment device for the anesthesia airway portion of the procedure. They will be informed that use of the device will not affect or influence their medical care. No specific gender, age, race, or ethnicity criteria will be used in the recruitment of subjects. The goal is to recruit 150 patients over weeks 1-6 of the study. We anticipate full recruitment during this time. Patient participation after completion of the study intervention in the operating room will be in the form of a survey with the goal for survey completion within 1-week of the intervention. Patients will be recruited solely on a voluntary basis with the option to withdraw at any time from the study without any form of penalty. This study is voluntary and no compensation or additional incentives will be provided.

